Design. A group of 6 hemianopic participants will be pre-screened for suitability and baseline (pre-training) performance will be acquired on the battery of visual tasks (see below) and be administered the low-vision visual functioning questionnaire (LV-VFQ-48) to assess quality of life, a dilated ophthalmic exam including Optical Coherence Tomography of the macula/RNFL, a kinetic visual field test with size V, and a 30-2 humphrey visual field with Size V. If the participant has a recent 30-2 exam on file, this may be used instead of collecting a new exam. Participants will receive a second kinetic visual field test and a 30-2 visual field test at the end of the study to measure any changes according to the clinical standard.

They will participate in weekly sessions (1.5-2 hrs) for the next three months. This purposely extends well beyond the window of expected recovery. In initial (“training”) sessions, subjects will be exposed (and respond) to spatiotemporally congruent pairs of visual-auditory stimuli presented within their blinded field, with occasional probes of unisensory visual stimuli on both sides of space. Once recovery of visual responsiveness in the contralesional field is observed, sessions will alternate between “training/testing” and “testing only” sessions in which performance on the visual battery will be re-assessed. Because this is a pilot study, the testing battery is extensive. However, the principal hypotheses and predictions are qualitative: subjects will either be able to perform a visual task at some level or not at all.

A high-speed digital video camera mounted behind the participant will record overt movements for later analysis using manual or automated scoring. The subject’s face is not included on the video, however, the video obtained contains potentially identifying information and will be secured on an encrypted drive. Multiple data points will be extracted: latency of the initiation of the motor movement, during of execution, and final position. These multiple measures will then be analyzed alongside other data points for the subject after anonymization to determine their changes during the course of experimentation and prognostic value in treatment outcomes.

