Apparatus. The perimetry apparatus (similar to that used for animals, scaled for humans) consists of a ~2m diameter semicircular arena with independently-controlled LEDs (space 2.5°) and speakers (spaced 10°) subtending the central 180° of space embedded in the arena wall. Subjects are seated with their chins in a rest while their eyes are tracked by a high-speed camera (ISCAN ETL200). They acquire fixation of a central spot to initiate a trial (but are not forced to maintain fixation during stimulation). They then make saccades to visual or auditory targets as they appear. Latency of movement and final eye position are recorded. All training, and the training/testing of low-level tasks, takes place in this apparatus. A complementary virtual reality (VR) apparatus provides a platform for training and for testing both low-level and high-level vision, and consists of an HTC Vive Eye Pro with eye-tracking capabilities. Custom software developed in C++ and the Unreal Framework presents visual and auditory stimuli within an immersive 3-D environment. Manual HTC controllers are used to control a set of virtual hands to “point” to targets, with latency and final position of eye, gaze, and hand all tracked and recorded. A microphone records subject verbal responses of confidence in both apparatuses. The VR apparatus provides great flexibility in the delivery of training and testing stimuli, and may be used in either setting.

Multisensory training: Multisensory training is accomplished in the perimetry apparatus under dark (.001 lux) and quiet (~30 dB) ambient conditions. Each session begins with 10 mins of briefing and

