Informed Consent. Written informed consent will be obtained. The risk of harm or discomfort that may occur as a result of taking part in this research study is not expected to be more than in daily life or from routine physical or psychological examinations or tests. The rights and welfare of study will be protected

through the use of measures to maintain the confidentiality of study information. Study results will be presented or published in lieu of providing individual subjects additional information regarding the study.

Confidentiality and Privacy. Confidentiality will be protected by collecting only information needed to assess study outcomes, minimizing to the fullest extent possible the collection of any information that could directly identify subjects, and maintaining all study information in a secure manner. To help ensure subject privacy and confidentiality, only a unique study identifier will be used during data collection. Following data collection individual subject files will be destroyed within 5 years and converted to an anonymous generalized analytical data set. Data access will be limited to study staff. Data and records will be kept locked and secured, with any computer data password protected.

Data and Safety Monitoring. The principal investigator will be responsible for the overall monitoring of the data and safety of study participants. The principal investigator will be assisted by other members of the study staff.

Reporting of Unanticipated Problems, Adverse Events or Deviations. Any unanticipated problems, serious and unexpected adverse events, deviations or protocol changes will be promptly reported by the principal investigator or designated member of the research team to the IRB and sponsor organization if appropriate.

References

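### Movement measures taken from video have no masking of the scorer to session and no fixed scoring method, so scoring drift could be read as change over training

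*Combined protocol and SAP*

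**What the plan says.** Under Methods and Measures, Design, a camera behind the participant films body movements "for later analysis using manual or automated scoring". Three quantities are extracted: "latency of the initiation of the motor movement, during of execution, and final position" (the second evidently means duration). Their purpose is "to determine their changes during the course of experimentation and prognostic value in treatment outcomes".

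The nearest provisions to a safeguard are these:

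- Design: "These multiple measures will then be analyzed alongside other data points for the subject after anonymization".
- Confidentiality and Privacy: "only a unique study identifier will be used during data collection", and "Data access will be limited to study staff".

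The document does not say who scores the video, when each method applies, whether one method is kept throughout, whether the scorer can see the session number or date, or how agreement between scorers is checked.

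Other data streams are described separately. Under Apparatus, the perimetry set-up has an eye tracker, and "Latency of movement and final eye position are recorded". The virtual-reality set-up tracks latency and end position of eye, gaze and hand by device.

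**The concern.** Reading movement onset or end point from video by hand involves judgement. A scorer who knows that a clip is from a late session, and who expects recovery, may read it differently from an early one. A move from hand scoring to software partway through the study could also shift the readings.

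The design has no concurrent control group, so the evidence for change is the comparison of later with earlier sessions within subjects. A scoring shift that follows session order cannot be separated from an effect of training. Adding trials does not help, because a systematic shift does not average out.

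At stake is whether reported changes in the video measures, and any prognostic use of them, can be trusted. That has some weight even in a pilot, because the results are meant to support funding and larger trials, and the Analytical Plan intends its parameter estimates to inform later studies.

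**Working it through.** The plan gives no figure for scoring error, so there is nothing to reproduce. The check sets the relevant sections side by side.

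**1. Does any provision hide the time point from the scorer?** No. In Design, anonymization is attached to the analysis, which follows extraction of the measures, and it concerns identity. A study identifier does not conceal the visit. Restricting access to study staff does not create a masked reader.

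**2. Does any provision hold the method constant?** No. Two methods are named without a rule for choosing. The regression in the Analytical Plan examines change over time, subject and side of space, and names no term for scorer or method. It includes latency without saying whether the video is a source.

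**3. Does the intact side act as a control?** Partly. Visual tests covers both sides of space and the Analytical Plan compares them, so a general drift would also appear on the intact side. But the direction of movement is visible on video and the lesion side is fixed within a subject. An expectation of recovery could therefore act on the blind side alone.

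**4. Which results are exposed?**

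| Result | Source | Exposed? |
|---|---|---|
| Eye latency and end position, perimetry | Eye tracker (Apparatus) | No |
| Eye, gaze and hand latency and end position, virtual reality | Device (Apparatus) | No |
| Correct or incorrect at <10° | Tone within the trial (Visual tests); online tracking (Confidence reports) | No |
| Overt-movement latency, duration, end position | Video, scored later (Design) | Yes |

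Apparatus does not list duration among the instrument measures, so video is its only stated source. Interventions and Interactions allows pointing gestures, and no hand tracker is described for the perimetry set-up.

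**5. Scale, on assumptions only.** Take n = 6, no true change, a two-sided 5% paired t-test of early against late sessions, and the same scoring shift in every subject, equal to k SDs of the within-subject change. The test statistic is then noncentral t with n − 1 = 5 degrees of freedom and noncentrality k√6.

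| k (assumed) | k√6 | Chance of declaring a change |
|---|---|---|
| 0 | 0 | 5.0% |
| 0.25 | 0.61 | 8.0% |
| 0.5 | 1.22 | 17.1% |
| 1.0 | 2.45 | 50.7% |

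The plan does not name this test, and the documents give no value of k. The table shows only how sensitive a six-subject before-after comparison is to a systematic shift.

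**6. Scoring load.** Multisensory training gives 500–1000 paired presentations plus 200–400 other trials, that is 700–1400 per session. (One trial per 5 seconds for 60 minutes gives 3600/5 = 720, near the lower end.) If there were 12 such sessions (assumption) for 6 subjects, the lower end gives 700 × 12 × 6 = 50,400 trials. Not every session is of this type, and the plan does not say that every trial is scored from video, but the number of clips could be large.

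**The case against.** The strongest reply is that the video is supplementary. The camera is behind the participant and the face is out of frame, so it should not be the source for eye landing position, and saccades are the response requested in training. Instruments record latency and position for the eye, and for the hand in virtual reality. The main hypotheses ask whether a task can be done at all. All of this stands, and it confines the point to secondary measures.

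Four stronger readings are tempting, and the documents do not support them:

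- **That lenient video reading would inflate the share of responses within 10°.** Correctness is signalled within the trial and tracked online, before any later video scoring.
- **That scorers know the session, or that the method changes from clip to clip.** The text does not prevent either, but states neither. Its wording fits equally well with one method chosen for the whole study.
- **That any scoring bias must coincide with training time.** This requires drift or switching that follows session order, which is possible but not documented.
- **That masking is the only protection.** Consistent automated scoring, instrument cross-checks and the intact side each help in part.

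It is also fair to say that masking would be imperfect and would take work. Design places training first and testing sessions after recovery is seen, so task content may reveal study phase. These objections limit the claim; they do not supply the missing rule.

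**Conclusion.** The gap is real and small. The plan lets overt-movement latency, duration and final position be scored by hand and analysed for change over time, with neither masking to session nor a single-method rule, in a design where an ordered scoring shift would be confounded with training. Neither the size nor the direction of any bias can be found from the documents; the false-positive rates above rest wholly on assumed shifts and a test the plan does not specify.

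The conclusion assumes that at least some video will be scored by hand, or that the method could differ between sessions. If one automated method were used throughout, little would remain. The point does not call into question the instrument-recorded measures, task correctness or the qualitative main hypotheses. It is a cheap improvement and not a flaw in the main result.

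**What to change.** Add a short statement to Design:

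- Choose one scoring method for each video measure and use it for all sessions and subjects.
- Where scoring is manual, give scorers clips under random codes, shuffled over sessions within a subject, without session number or date.
- Link codes to sessions only after the scored file is locked.
- Where an instrument records the same measure, use it as a cross-check.

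**Cost.** A renaming script and a few sentences. The same staff can score, and no participant procedure changes because scoring is done later from stored video.

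**Downsides.** Manual scoring of a subject has to wait until that subject's last session. Handling the clips takes real work given the number of trials; scoring a random sample of clips per session would contain it. Task content or a visible headset may still partly reveal the study phase, so the masking reduces expectation bias without removing it.

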apparatus calibration. Each trial begins after subjects fixate for 500 ms on a central fixation spot. After a brief (300-600 ms) delay, either a training stimulus (3 f.c. bright light from LED + 75 dB broadband sound from speaker) is activated at 45° of eccentricity in the blind field, or (with lower frequency) a single visual stimulus with same parameters is activated at 45° in the intact or blinded field, or no stimulus is presented at all. Subjects are requested to saccade to any stimuli that appear and otherwise maintain fixation. Stimuli remain active for 3 seconds or for 500 ms after a saccade is made, whichever is shorter. Multisensory training the VR apparatus uses an identical procedure, with the visual and auditory stimuli being an equivalent stimuli produced at the same virtual distance and positions. Trials are presented at a rate of 1/5 sec and continue for 60 mins. Depending on whether it is a purely training or training/testing session, this allows for 500 – 1000 presentations of the visual-auditory training stimulus per session along with 200-400 trials containing single visual or no stimuli. This greatly exceeds the number required in the animal model, and provides the best opportunity for success in sessions of practical duration.

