Visual tests: Tests of vision will be conducted on both sides of space and are organized in trials. In each trial the subject acquires fixation for 500 ms before a stimulus is presented after a randomized delay (200-600 ms). Subjects are required to saccade or point to (i.e., “indicate”) the stimulus or stimulus-target (<10° error) within 2 seconds or their response is scored as a “No-Go”. They are informed of whether their response was “correct” or “incorrect” via an auditory tone after a confidence report (see below). Each test has one or more stimulus levels that are manipulated to create the independent variable(s) of psychometric functions of performance. Detection/Localization: Trials contain either a visual target (LED or 5X5° white square) of manipulated contrast at a randomly-selected location outside of central space (correct response: indicate), or no stimulus anywhere (correct response: No-Go). Competition: Trials contain either no stimuli (correct response: No-Go), or 1 stimulus at a randomly-selected location on either side of space (correct response: indicate), or 2 identical visual stimuli at homotopic locations with randomized eccentricity (correct response: indicate both). Stimulus contrast is manipulated. Multisensory Integration: Trials contain either no stimuli (correct response: No-Go) or brief (100 ms) low-contrast visual or low-volume auditory stimuli presented alone or together at a randomly-selected location (correct response: “indicate”). This evaluates whether the senses can be used synergistically in contralesional space to enhance localization as in intact subjects. Frequency Discrimination: Pairs of oriented gratings with manipulated Δ° and Δf presented on either side of space (correct response: indicate if same, No-Go if different). Shape Discrimination: Unilaterally-presented pairs of simple Efron shapes (see (Whitwell et al., 2014)) with manipulated similarity (correct response: indicate if same, No-Go if different). These shapes consist of stacked rectangles or smoothed splines whose similarity can be quantitatively manipulated and provide a robust, common, and controlled way of assessing shape perception in normal and compromised populations. Subjects will also have the opportunity to report qualitative aspects of any changes in their visual perception during the study.

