Outcome Measure(s). A variety of dependent measures are extracted during these experiments, including responses selected, response delay/timing, response accuracy, etc. Responses to visual stimuli will be evaluated over the duration of the experiment to assess recovery of function. The main hypotheses state that subjects will either be able to perform some task at some level or not at all, although there is likely to be quantitative variation in parameters such as response latency, threshold sensitivity, and confidence. In this context, recovery of any visual function is a success. Below we outline two sets of predictions identifying the most credible outcomes and elaborate on the significance of each, although mixed results are also possible.

Modest Rehabilitation: It is possible that hemianopic patients will recover basic reflexive visual functionality, but their capabilities will be limited to those typically associated with “blindsight”. In this case, they would be able to detect and localize visual stimuli in the rehabilitated field and use auditory information to enhance this capability. However, they would always choose the intact field in competition tasks, be unable to perform any higher-order discriminations in the contralesional field, and would always

have low confidence in that field even when they can perform visually – a result falling short of that seen in the animal model. Such a result will be less than expected but is not without clinical value: by acquiring the ability to respond to contralesional visual stimuli, rehabilitated subjects can bring them into the sighted field for further analysis.

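### Gaze is free once a test stimulus is on and no scoring rule uses gaze, so search or inspection with the sighted field can be counted as blind-field success

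*Combined protocol and SAP*

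**What the plan says.** All references are to the combined protocol and SAP.

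- **Apparatus.** For the perimetry arena, the text on participants reads "They acquire fixation of a central spot to initiate a trial (but are not forced to maintain fixation during stimulation". The arena is used for training and low-level tasks. The virtual reality apparatus also serves high-level tests and has no fixation rule of its own. Both apparatuses record latency and final eye position.
- **Visual tests.** The common rule is "In each trial the subject acquires fixation for 500 ms before a stimulus is presented after a randomized delay (200-600 ms"; nothing is said about gaze after onset. Participants must saccade or point to the target, with less than 10° error, "within 2 seconds or their response is scored as a" No-Go. The only stated stimulus duration belongs to Multisensory Integration: "brief (100 ms) low-contrast visual or low-volume auditory stimuli presented alone or together". Detection/Localization, Competition, Frequency Discrimination and Shape Discrimination have none.
- **Multisensory training.** The only other duration given is for training: "Stimuli remain active for 3 seconds or for 500 ms after a saccade is made, whichever is shorter". There, the stimulus outlasts the gaze shift.
- **Outcome Measure(s).** A Modest participant would always choose the intact field in Competition, would "be unable to perform any higher-order discriminations in the contralesional field" and would always have low confidence there. The same paragraph gives the clinical value of that outcome: "rehabilitated subjects can bring them into the sighted field for further analysis". The Expected participant can do every task at some level.
- **Analytical Plan.** Psychometric functions are fitted per subject and location or side of space. No gaze-referenced location, fixation-break rule or trial exclusion is mentioned.

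**The concern.** Hemianopia moves with the eyes. A stimulus on the blind side of the room is in the blind field only while gaze stays near centre. Once gaze passes beyond the stimulus, or close enough to bring part of it across the midline, sighted vision can be used. The plan scores by side of space, so such a trial counts as a blind-side success.

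The protocol itself expects Modest participants to use eye movements in this way, yet identifies them by failure on discrimination and by low confidence. A participant who detects something, orients to it, inspects it and answers correctly with high confidence would show the Expected pattern on both markers without any discrimination in the blind field. The planned criterion is qualitative (able at some level, or not at all), so a limited number of such trials could change the conclusion for a participant. There are six participants and no untrained comparison group, so scanning gains cannot be subtracted.

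**Working it through.** The documents give no power, effect size or numerical criterion for this point, so there is no stated figure to reproduce. Two checks were made.

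**1. Is there time to look?**

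From the document: a 2 s response window. Assumed: saccade latency plus flight time from 150 + 80 ms to 400 + 200 ms.

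- Fast case: 2000 − 230 = 1770 ms left after the first shift; 2000 / 230 allows 8 whole shifts.
- Slow case: 2000 − 600 = 1400 ms left; 2000 / 600 allows 3 whole shifts.

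If the stimulus stays on, there is ample time to inspect it. A 100 ms stimulus ends before the shortest assumed latency of 150 ms, so Multisensory Integration is protected. That test does not separate the two outcomes, because both predict success on it.

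**2. How far could discrimination scores move?**

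This applies where the answer is not itself a saccade. Take a participant whose blind-field same/different accuracy is 0.5. Let *s* be the share of trials with a gaze shift, *d* the probability of detecting that something is there, and *a* the accuracy of sighted vision. Then

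p = 0.5 + s × d × (a − 0.5).

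Assumed: d = 0.6 to 0.95, a = 0.8 to 0.9, and an illustrative one-sided 5% exact binomial criterion against 0.5. Block sizes of 24 and 96 lie within the 20 to 96 trials given under Testing structure. The criterion is at least 17 of 24, or at least 57 of 96.

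Example, s = 0.5: lowest p = 0.5 + 0.5 × 0.6 × 0.3 = 0.59; highest p = 0.5 + 0.5 × 0.95 × 0.4 = 0.69.

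| Share of trials with a shift | p correct | P(labelled able), 24 trials | P(labelled able), 96 trials |
|---|---|---|---|
| 0 | 0.50 | 0.032 | 0.041 |
| 0.25 | 0.545–0.595 | 0.08–0.18 | 0.20–0.55 |
| 0.5 | 0.59–0.69 | 0.17–0.52 | 0.51–0.98 |
| 1 | 0.68–0.88 | 0.48–0.995 | 0.97–1.00 |

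For comparison, a participant who holds fixation and has true blind-field accuracy of 0.7 to 0.8 would be labelled able with probability 0.57 to 0.91 (24 trials) or 0.99 to 1.00 (96 trials). When shifts are common, accuracy alone does not tell the two apart.

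**3. Where the answer is a saccade.** In both discrimination tests the participant indicates if the items are the same and withholds if they differ. If an inspecting saccade is itself scored as indicating, inspecting every trial gives accuracy equal to the proportion of same trials: 0.50 if half are the same (assumed). The table therefore does not apply to saccadic answers.

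**The case against.** The case against a stronger claim is substantial, and most of it stands.

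- **Scope of the quoted rule.** It describes the arena, while high-level tests are described for virtual reality. Free gaze in those tests is an inference from silence. This stands, although the pre-onset rule under Visual tests covers the whole battery and adds nothing after onset. The remark under Interventions and Interactions that failing to fixate can abort the experiment concerns participant control and does not supply a scoring rule.
- **Detection by saccade.** A saccade is an intended response. Onset follows central fixation at a random location, with no-stimulus trials included, so a prompt and accurate first saccade is good evidence of blind-field vision. This stands. Late or searching saccades are not such evidence, and no rule separates them.
- **A reader might infer that the two outcomes become indistinguishable.** The documents do not support that. Eye latency and final position are recorded, first-saccade direction in Competition remains informative, and kinetic and 30-2 fields before and after training give a separate reading of detection. The fields do not test discrimination or confidence, however.
- **A reader might infer that every blind-side discrimination success could be spurious.** The saccade-scoring point above defeats this as a general bound.
- **A reader might infer that training must raise scanning and so bias the change from baseline upwards.** This is plausible, since correctness tones and the points wager reward any strategy that works. It is not shown: in training, participants are asked to hold fixation when nothing appears, and scanning already present at baseline would affect baseline scores too.
- **Stakes.** Modest and Expected are descriptive predictions, mixed results are allowed, and recovery of any visual function counts as success. This limits the consequence, but a blind-field success still has to be one.

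**Conclusion.** The concern holds in a limited form. The stated scoring can credit the blind field with performance obtained by search or, for pointing and verbal answers, by sighted inspection. The discrimination and confidence markers are the most exposed; the arithmetic covers discrimination only, and the effect on confidence is reasoned rather than calculated.

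The size is not determined by the documents. Under the assumptions above, the chance that a participant with no blind-field discrimination is labelled able in a 24-trial block rises from 0.032 with no gaze shifts to 0.17–0.52 with shifts on half the trials. For 96 trials it rises from 0.041 to 0.51–0.98. These ranges depend on assumed detection, sighted accuracy, shift frequency and the 5% criterion, on the stimulus remaining visible after the shift, and on free gaze in virtual reality. They do not establish that the trial would misclassify anyone; they show that the plan has no rule to prevent it.

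**What to change.** State the stimulus duration for every test, and prespecify the following before testing starts:

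- **Both apparatuses:** keep the full gaze trace from the existing eye trackers. Latency and final position alone may not show where gaze was while the stimulus was viewed.
- **Detection/Localization:** count as blind-field successes only trials on which the first saccade after onset goes to the target within a prespecified latency.
- **Frequency and Shape Discrimination:** take a pointing or verbal response, as Interventions and Interactions already permits. Count as blind-field trials only those with gaze near fixation, within a prespecified window, until stimulus offset or response; alternatively, end the stimulus when gaze leaves that window. Report the remaining trials, with their confidence scores, separately.
- **Competition:** keep the requirement to indicate both targets, and also report first-saccade direction.
- **Training trials:** no change.

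A blanket 100 ms presentation or first-saccade-only scoring across the battery is not advised. The former leaves little motion in the moving-stimulus condition, and the latter makes the two-target Competition response unattainable by eye.

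The cost is some excluded or repeated trials, and a little more analysis work. If gaze-contingent offset is chosen, a software change is also needed. No new equipment is required.
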